### **3.5.5 Duration of Participation**

Full participation in the study will last a minimum of 34 weeks from the baseline visit to the completion of the N-of-1 trial. Participation may last more than 34 weeks if a family experiences delays at any phase of the study.

## **3.6 Statistical Plan**

### **3.6.1 Sample Size Determination**

The primary goal of Aim 1 is to determine effectiveness of the SCD vs. modified SCD vs. usual diet for an *individual* patient. Because the focus is on the immediate decision of which treatment to select, or if the treatments were different than the patient's usual diet, it is not necessary to protect against a false-positive decision as in standard hypothesis tests used in clinical trials; thus sample size calculations are not recommended for individual N-of-1 trials. For obtaining an estimate of the population average effects of the SCD vs. modified SCD on improving symptoms, a total of up to 60 patients will participate in the two- treatment crossover study. Using the weekly PROMIS pain interference T-score measure (standardized mean of 50 and standard deviation of 10) and incorporating aspects of the design related to the number of planned crossovers, washout periods, and autocorrelation from repeated measures, we will have 90% power with a two-sided 5% alpha to detect a mean difference of 3 points between groups which corresponds to the minimally important difference on the PROMIS measures, except in the case when  $\sigma_t = 5$  and  $\rho > 0.5$  when the minimal detectable difference is above 3 to obtain 90% (but not 80% power).

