## 1 Aim 1 Summary

Title	Personalized Research On Diet in Ulcerative Colitis and Crohn's Disease
Short Title	PRODUCE Study
Protocol Number	2017-0683
Methodology	Series of N-of-1 trials
Study Duration	4 years
Study Centers	Multi-center with estimated 21 centers
Objectives	Use a series of N-of-1 trials to determine the effectiveness of a specific carbohydrate diet (SCD) in reducing symptoms and inflammatory burden in patients with IBD versus a modified SCD at both the individual and population level.
Number of Participants	Up to 60 recruited across all sites
Diagnosis and Main Inclusion Criteria	Age 7-18 years; IBD; Stable medications
Statistical Methodology	Analysis of individual trial results using Bayesian models to estimate treatment differences; Meta-analysis of series of N-of-1 trials using multilevel mixed models

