### **3.5.4 Early Withdrawal of Participants**

If a patient experiences symptom flare, leading to either the diet intervention being stopped, medication being changed, or the need for surgical intervention, their participation in the N-of-1 protocol will be discontinued. In addition, patients who become pregnant during the study will be automatically withdrawn, as will patients that have  $\geq 7.5\%$  nonintentional weight loss. Patients may also withdraw if they feel that they are unable or unwilling to continue the assigned diet or data collection. Participants will be dropped from the study if they have a symptom tracking response rate of  $<50\%$  in the baseline period that does not improve after reasonable attempts by research coordinators (as outlined in the study SOPs) to assist participants in improving data collection. Because completion of stool fecal calprotectin is required to advance from one treatment period to another, a participant who never collects and sends in a stool specimen will be dropped at that point in the study. All data from such participants will be retained and analyzed. Patients who wish to terminate a treatment period early (and switch to the next assigned treatment) will not be considered withdrawals. Participants who wish to end their study participation early, but have completed at least two full diet treatment periods (i.e., A1 and B1), will have the option to discontinue participation and terminate the protocol early. Participants who choose to discontinue from the study in these instances will schedule a time to come into clinic to

receive their final study results and complete the end of survey questionnaire regarding their N-of-1 experience. These participants will not be considered withdrawals.

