of the (1) difference in efficacy between the two diets; and (2) probability that each treatment is better than the other; as well as the (3) difference in efficacy between each diet and the baseline level; and (4) probability that each treatment is better than the baseline. Results will be portrayed numerically and graphically. We will develop educational materials to aid patients and clinicians in interpretation (Appendix B). Posterior probabilities of outcomes will be calculated using an interface that incorporates open-source R software interfacing through Rjags with open-source JAGS software. The R code creates the Bayesian model, loads the stored data and chooses intelligent starting values that are then fed into JAGS to return the Markov chain Monte Carlo (MCMC) simulations of the joint posterior distribution. The R package will accept input from the Eureka platform to construct models and return results back to Eureka for display.

Statistical analyses will be completed and patients will be given results of their individual N-of-1 studies if they complete at least one paired treatment period and there is enough data in both treatment periods to perform valid statistical analysis.

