**Missing data:** Based on our experience, the overall completion rates of daily symptom trackers and weekly surveys by ICN patients and parents is >80%, we have found that when participants are working on a specific test or personal experiment with their physician, adherence increases to >90%. In cases of missing outcome data, we will ignore the missing values in the analysis of individual N-of-1 trials which is equivalent to treating them as being missed at random since the analysis is not adjusted for covariates. In the meta-analysis, we will explore the association of missingness with observed variables and condition analyses on these variables as appropriate. We will also explore treating the missing observations as latent parameters and estimate them as part of the Bayesian model assuming them to be missing at random. If patients decide to stop a treatment before 8 weeks, we will analyze the data available. Since effect modifiers in the meta-analysis are collected at the patient level, we expect them to be completely collected (e.g., there will not be a need for a statistical approach to address missing data for these variables). In the meta-analysis, we will perform the following sensitivity analyses for different types of missing data:

(1) analysis of all available data; (2) analysis excluding patients who withdrew early from the trial; (3) analysis of patients who completed the entire protocol, i.e. excluding those who withdrew early and those who terminated any treatment periods early.

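### Does the 90% power in section 3.6.1 fail because it names no allowance for patients who leave early?

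*Combined protocol and SAP*

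**What the plan says.** Section 3.6.1 sizes the population comparison of the two diets on the weekly PROMIS pain interference T-score. It gives a standardised SD of 10, a ceiling of 60 patients, and this claim: "we will have 90% power with a two-sided 5% alpha to detect a mean difference of 3 points between groups". The calculation is described as "incorporating aspects of the design related to the number of planned crossovers, washout periods, and autocorrelation from repeated measures". One exception is disclosed, at σ_t = 5 with ρ above 0.5, "when the minimal detectable difference is above 3 to obtain 90% (but not 80% power"). The summary in section 1 gives the number of participants as "Up to 60 recruited across all sites".

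Section 3.5.4 covers early exit. After a flare that stops the diet, changes medication or needs surgery, "their participation in the N-of-1 protocol will be discontinued". Pregnancy, unintentional weight loss, poor baseline tracking, a stool sample never sent, or the family's own choice can also end participation. "Participants who wish to end their study participation early, but have completed at least two full diet treatment periods" may stop there without counting as withdrawals. The same section keeps and analyses the data of patients who leave.

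Section 3.6.2 gives individual results to patients "if they complete at least one paired treatment period" with enough data. Its sensitivity analyses include one of patients who completed everything, "excluding those who withdrew early and those who terminated any treatment periods early".

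**The concern.** The listed inputs are planned crossovers, washout and autocorrelation. Loss of patients is not among them, and 60 is the most that can be recruited. A patient who never reaches the second diet gives no within-patient contrast, and one who stops after a single block gives a less precise one. The stated exception also suggests that the 90% limit lies near σ_t = 5, ρ = 0.5, where there may be little room for loss.

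The origin of the figure is unclear as well. The Document History reports a revised calculation when the number was cut to 50 (v4.8) and mentions none when it rose to 60 (v5.1). If the exception dates from 50 patients, it may not describe 60. This is the only power statement for the population-level comparison, so an optimistic figure would mislead readers about how firmly a null result can be read.

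**Working it through.** **Inputs from the plan.** Difference 3, two-sided 5%, power 90%, up to 60 patients (3.6.1). Four 8-week periods (3.3.1), first weekly score of each dropped (3.6.2), leaving 7 per period.

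**Assumed, because the plan does not say.** σ_t is the SD of true diet effects across patients. ρ is first-order autocorrelation between weekly scores. σ_w is the within-patient SD.

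**Can the 90% be reproduced?** No. A parallel comparison of 30 against 30 with SD 10 gives Φ(3/(10√(2/30)) − 1.96) = 21%, so a within-patient model must have been used. For that model:

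S² = σ_t² + σ_w²·V(ρ), power = Φ(3/√(S²/N) − 1.96)

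90% power needs 3/√(S²/N) ≥ 1.960 + 1.2816 = 3.2415, so S² ≤ N × (3/3.2415)² = 0.8565 N. That is 51.39 at N = 60 (S ≤ 7.17) and 42.83 at N = 50 (S ≤ 6.54). Without σ_w the check stops there.

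**Effect of loss if the limit is exactly 3.00.** With N0 the number at which power is 90%, power(n) = Φ(3.2415√(n/N0) − 1.96) and the detectable difference is 3√(N0/n). No SD is needed.

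| N0 | n | Power | Detectable at 90% |
|---|---|---|---|
| 60 | 54 | 86.8% | 3.16 |
| 60 | 48 | 82.6% | 3.35 |
| 60 | 45 | 80.2% | 3.46 |
| 50 | 60 | 94.4% | 2.74 |
| 50 | 50 | 90.0% | 3.00 |

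**Must the limit be exactly 3.00 at N = 60?** No. The plan says only that the detectable difference exceeds 3 when ρ is above 0.5. If ρ was examined on a grid, the crossing can lie anywhere between 0.5 and the next value.

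Take correlation within periods only: V(ρ) = [7 + 2Σ(7−k)ρ^k]/49 for k = 1 to 6, so V(0.5) = 0.3476, V(0.6) = 0.4227 and V(0.7) = 0.5182. With σ_t = 5, the share left for within-patient error is 51.39 − 25 = 26.39.

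- Crossing at 0.5: σ_w = √(26.39/0.3476) = 8.71. No reserve.
- Crossing at 0.6: σ_w = √(26.39/0.4227) = 7.90. At ρ = 0.5, S² = 25 + 62.4 × 0.3476 = 46.7, the detectable difference is 3.2415√(46.7/60) = 2.86, and 46.7/0.8565 gives 55 patients for 90%.
- Crossing at 0.7: σ_w = √(26.39/0.5182) = 7.14. At ρ = 0.5, S² = 25 + 50.93 × 0.3476 = 42.7, the detectable difference is 2.73, and 42.7/0.8565 gives 50 patients.

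So if the next grid value is 0.7, any σ_w from about 7.1 to 8.7 gives the stated exception at σ_t = 5. If σ_t = 4 was also examined, the top of that range drops to √((51.39 − 16)/0.5182) = 8.26, since a larger σ_w would create a second exception. The low end, where the reserve lies, is unaffected.

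With correlation running across the whole series, V(0.5) = 0.3175 and V(0.7) = 0.3831. A crossing at 0.7 then gives σ_w = 8.30, a detectable difference of 2.87 at ρ = 0.5, and 55 patients.

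**What a one-block patient adds.** One block doubles the within-patient error term. At σ_t = 5, ρ = 0.5 and σ_w = 7.14 (within-period correlation), S² goes from 25 + 17.7 = 42.7 to 25 + 35.4 = 60.4, so the patient carries 42.7/60.4 = 71% of a completer's weight.

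**Away from the corner.** At σ_t = 3, ρ = 0.5 and even σ_w = 10 (whole series), S² = 9 + 31.75 = 40.75, and 40.75/0.8565 gives 48 completers for 90%.

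**The case for a change.** The strongest reply is that a flat 90% with no visible basis should not stand. Two sets of inputs reproduce the exception with whole-series correlation: σ_w = 9 at N = 60 (detectable differences 2.98, 3.08 and 3.13 at ρ = 0.5, 0.6 and 0.7), and σ_w = 7.5 at N = 50 (3.00, 3.08 and 3.13). Under the first, modest loss breaks 90% at the corner. Under the second, the exception vanishes with 60 patients, where the largest of the three values is 2.86. The only SD printed, 10, does not fit at N = 60: the detectable difference is already 3.03 at σ_t = 5, ρ = 0.4. An assumed loss of 10% before the second diet and 20% after one block leaves 84–86% power at σ_t = 5, ρ = 0.5 with σ_w = 9.

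What stands is that a reader cannot verify the 90% or its exception, and that no loss allowance is stated. What does not stand is the step to a wrong figure. An assumption of no loss is inferred from silence. The two readings are not exhaustive, as the grid argument shows. With σ_w = 7.5 the same assumed losses leave 90–91%. The history entries are context only: adequate power was the argument for the cut to 50, and no argument is recorded for 60. The analyses that exclude early leavers are sensitivity analyses and need no power claim of their own.

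**Conclusion.** No change to the plan follows. The paragraph leaves out detail that the sponsor's statisticians hold, and no stated number is shown to be wrong. At σ_t = 5, ρ = 0.5, the number of full completers needed for 90% runs from about 50 to 60 if the calculation was done at N = 60, and is about 50 if the limit was set at N = 50. The tolerable loss at that corner is therefore between none and about 10 of 60 (17%), and larger at smaller σ_t. These limits depend on how σ_t and ρ are read, on the correlation structure, and on a next grid value for ρ of no more than 0.7.

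The plan already discloses a case below 90%, keeps partial data, and defers analytic detail to a separate document. Its stated primary goal is the individual comparison, for which 3.6.1 makes no power claim. The population model, the patients analysed and the conclusions drawn would be the same with the inputs written out, and the posterior distributions will show the precision actually reached.

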### **3.6.2 Statistical Methods**

An overview of the statistical analysis can be found below. A formal data and statistical analysis plan will be prepared as a separate document

*Analysis of Individual N-of-1 Trials:* For the first treatment period only, there will be a 1-week run-in period as the participant gradually transitions from their usual diet to the intervention diet. A gradual transition is not needed beyond the first treatment period. For the first period, we will discard the first 7 days of data including the first weekly measurement. Based on clinical experience we expect that diet effects on symptoms wash out by 1 week. Thus, for all subsequent treatment periods we will discard the first 7 days of data including the first weekly measure during each treatment period. At the end of each person's N-of-1 trial, statistical analysis will be performed to compare results on the two treatments. Each N-of-1 trial requires a separate analysis which is automated to run in the background once each trial is completed. The analysis consists of running Bayesian models that compare the average response on each of the two treatments and baseline diet. Models will incorporate the appropriate scales for the outcomes (e.g. normal distributions for continuous variables, multinomial distributions for categorical variables) and the appropriate representation of the function linking the expected outcome to the predictors (e.g., cumulative logit link for ordinal outcomes).

Results will be reported for all study measures (stool frequency, stool consistency, PROMIS Pain interference, PROMIS GI Symptoms, fecal calprotectin) to enable patients to weigh symptoms that are most important to them. For each outcome, each patient will be provided with an estimate

## USING SINGLE SUBJECT (N-OF-1) DESIGNS TO ANSWER PATIENT-IDENTIFIED RESEARCH QUESTIONS – AIM 1

of the (1) difference in efficacy between the two diets; and (2) probability that each treatment is better than the other; as well as the (3) difference in efficacy between each diet and the baseline level; and (4) probability that each treatment is better than the baseline. Results will be portrayed numerically and graphically. We will develop educational materials to aid patients and clinicians in interpretation (Appendix B). Posterior probabilities of outcomes will be calculated using an interface that incorporates open-source R software interfacing through Rjags with open-source JAGS software. The R code creates the Bayesian model, loads the stored data and chooses intelligent starting values that are then fed into JAGS to return the Markov chain Monte Carlo (MCMC) simulations of the joint posterior distribution. The R package will accept input from the Eureka platform to construct models and return results back to Eureka for display.

Statistical analyses will be completed and patients will be given results of their individual N-of-1 studies if they complete at least one paired treatment period and there is enough data in both treatment periods to perform valid statistical analysis.

**Meta-Analysis of N-of-1 Trials:** The collection of individual N-of-1 trials can be thought of as a set of studies whose results can be combined as in a meta-analysis. The data can be considered as a multilevel structure in which a set of patients is studied with each patient having a set of measurements. Standard multilevel mixed model methods will be used to estimate the average effect and variance within and across patients. Across patient values estimate the average effect in the population of patients studied, while the within-patient estimates describe an improved estimate of each patient's true effect assuming exchangeability across patients. We will fit these models using a Bayesian multilevel model with non-informative priors in order to obtain posterior distributions of the within and between effect sizes. We will then compare the multilevel patient estimates with those from the patient's data alone in order to determine how much the effects change and how much additional precision these estimates gain. We will also include between-patient covariates to account for variability and to test for heterogeneity of treatment effects (HTE). We hypothesize that HTE may exist based on age, sex, disease (CD or UC/IC), disease activity (mild or moderate), maintenance medication use, disease location, and disease type (inflammatory or penetrating). The model will include the baseline levels of the outcomes which will enable estimates of the effect of the study diets relative to the unrestricted diet. We will also fit models that adjust for trends over time and account for correlation and carryover. Analyses will use the appropriate probability distribution and link function for the outcome variable type (e.g. normal distributions for continuous outcomes and ordinal logistic regression with a cumulative logit link for scales).

**Missing data:** Based on our experience, the overall completion rates of daily symptom trackers and weekly surveys by ICN patients and parents is >80%, we have found that when participants are working on a specific test or personal experiment with their physician, adherence increases to >90%. In cases of missing outcome data, we will ignore the missing values in the analysis of individual N-of-1 trials which is equivalent to treating them as being missed at random since the analysis is not adjusted for covariates. In the meta-analysis, we will explore the association of missingness with observed variables and condition analyses on these variables as appropriate. We will also explore treating the missing observations as latent parameters and estimate them as part of the Bayesian model assuming them to be missing at random. If patients decide to stop a treatment before 8 weeks, we will analyze the data available. Since effect modifiers in the meta-analysis are collected at the patient level, we expect them to be completely collected (e.g., there will not be a need for a statistical approach to address missing data for these variables). In the meta-analysis, we will perform the following sensitivity analyses for different types of missing data:

(1) analysis of all available data; (2) analysis excluding patients who withdrew early from the trial; (3) analysis of patients who completed the entire protocol, i.e. excluding those who withdrew early and those who terminated any treatment periods early.

